4.1.2 Estimated Number of Patients

Moving forward, we anticipate as few as four and as many as 20 additional patients could be enrolled and treated in this trial. We expect approval of the use of the four already enrolled and treated patients to seed the model, which would bring the overall total range from 8- 24 patients. If the highest planned dose is successfully administered to subjects and assuming one subject per CRM-calculated dose level (10), and an additional 10 subjects will be entered at the CRM-estimation of the safe target dose ($10+10 = 20$). If all subjects develop DLTs, the CRM model would de-escalate both through the initial and the two lower dose levels involving no more than 4 subjects and the trial would be halted (Section 4.5) with a minimal accrual of 4 subjects. Assuming that no DLTs will be encountered, we expect that under optimal conditions only 20 subjects ($10+10$) will be enrolled and treated in this study. These numbers will be modified if the new patient data for seeding the model is approved and could even decrease.

Thus, the maximum number of subjects that we expect to enroll and treat in this trial would be 20, assuming that the CRM will adjust each dose after the first 2 or 3 subjects and as more subjects are enrolled to encompass the initial test range. On the other hand, the minimum number of subjects who could be enrolled in this trial would be 4 assuming 2 DLTs at Dose Level 1, and the CRM recommending one or two lower doses.

4.2 Definition of Dose-Limiting Toxicity

The Cancer Therapy Evaluation Program (CTEP) has published Common Terminology Criteria for Adverse Events, version 4.0 for the grading of adverse events experienced in clinical trials for anti-neoplastic agents. Any grade 3 or greater non hematologic toxicity as defined by NCI CTCAE v 4, and considered as being possibly, probably or likely related to M032 will be considered a Dose Limiting Toxicity (DLT). However, specific symptoms including seizures, neurologic deficits such as weakness, dysphasia or sensory loss are prominent in this patient population due to the fact that these tumors frequently disrupt the function of normal areas of eloquent brain. Neurologic symptoms from involvement of eloquent brain are commonplace; corticosteroid, radiation, and chemotherapies also produce pre-existing symptoms in almost all cases. The pre-existing conditions listed in the **Table** on the following page are acceptable for inclusion in the clinical trial, provided the subjects meet the other inclusion and exclusion criteria.

For all of these pre-existing conditions, DLTs will be defined as progressive involvement of neurological dysfunction not attributable to tumor progression and/or the development of life threatening symptomatology associated with the original baseline status.

Neurologic deterioration will not be considered dose-limiting if it resolves back to the patient's baseline within two weeks of completing treatment. For example, increased weakness or aphasia that occurs during the infusion will be treated with increasing steroid doses and/or slowing of infusion rates, but not treated as a DLT if symptoms improve to baseline within fourteen days of completing treatment. Because of the site of M032 inoculation, important additional events that will be considered dose-limiting toxicities if they are likely related to M032 include death, stroke, hematoma requiring surgery, untreatable neurologic deterioration, unresponsive systemic infection, and disseminated HSV infection.

Management of the above adverse events is outlined in **Section 5**.

The maximally tolerated dose (MTD) is the highest dose level below the maximally administered dose when dose escalation decisions are made according to the guidelines above. Enrollment will be stopped when the MTD is determined or the maximally planned dose is acceptably tolerated by six patients.

There will be a minimum twenty-four (24) day observation period between the first patient at each dose level and subsequent patients enrolled to allow for evaluation of potential toxicity. If no dose-limiting toxicity is seen with the first patient, the twenty-four day waiting period will be waived for the second and third patients at that dose level. If the incidence of DLT at any given dose level meets the criteria for dose escalation, there will be a waiting period of a minimum of 24 days before dose escalation occurs. The Medical Monitor, in conjunction with a duly chartered external Data and Safety Monitoring Board comprised of an Infectious Disease expert, a neurosurgeon familiar with oncolytic virus therapy, a neuro-oncologist familiar with oncolytic virus therapy and an expert in the use of molecular biology methods to detect and quantify Herpes Simplex Viruses in clinical

specimens, will evaluate the safety of each dose tested to determine whether the protocol may proceed to the next dose level.

CTCAE#	Body System	Event name	Definition of Grade 3 Toxicity	Rationale for inclusion
222	General disorders and administration site conditions	Gait disturbance	Disabling; limiting self care ADL	Many subjects with malignant glioma have gait disturbance as a result of chronic corticosteroid administration
494	Musculoskeletal and connective tissue disorders	Muscle weakness left-sided	Limiting self care ADL; disabling	Malignant glioma can produce muscle weakness due to interruption of motor function
495	Musculoskeletal and connective tissue disorders	Muscle weakness lower limb	Limiting self care ADL; disabling	Malignant glioma can produce muscle weakness due to interruption of motor function
496	Musculoskeletal and connective tissue disorders	Muscle weakness right-sided	Limiting self care ADL; disabling	Malignant glioma can produce muscle weakness due to interruption of motor function
498	Musculoskeletal and connective tissue disorders	Muscle weakness upper limb	Limiting self care ADL; disabling	Malignant glioma can produce muscle weakness due to interruption of motor function
527	Nervous system disorders	Ataxia	Severe symptoms; limiting self care ADL; mechanical assistance indicated	Malignant glioma itself and many of the anti-epileptics drugs used to treat seizures associate with this disease can produce ataxia that requires mechanical assistance
529	Nervous system disorders	Central nervous system necrosis	Severe symptoms; medical intervention indicated	Accepted treatments for malignant glioma (for example radiation therapy) can produce CNS necrosis that requires medical intervention such as corticosteroid administration
531	Nervous system disorders	Cognitive disturbance	Severe cognitive disability; significant impairment of work/school/life performance	Both malignant glioma and its accepted therapies (for example radiation therapy) can produce impairment of work/school/life performance
532	Nervous system disorders	Concentration impairment	Severe impairment in attention or decreased level of concentration; limiting self care ADL	Both malignant glioma and its accepted therapies (for example radiation therapy) can produce impairment in attention or decreased level of concentration that affects self care ADL
536	Nervous system disorders	Dysesthesia	Severe sensory alteration; limiting self care ADL	Malignant glioma can produce alterations in sensory function limiting self care ADL
545	Nervous system disorders	Headache	Severe pain; limiting self care ADL	Malignant glioma can result in intracranial pressure resulting in severe headaches
567	Nervous system disorders	Pyramidal tract syndrome	Severe symptoms; limiting self care ADL	Malignant glioma can produce dysfunction of the pyramidal tract
571	Nervous system disorders	Seizure	Multiple seizures despite medical intervention	Malignant glioma can produce multiple seizures despite medical intervention
575	Nervous system disorders	Stroke	Severe neurologic deficit	Malignant glioma can produce stroke through its associated hypercoagulative state. Also, treatment for malignant glioma (for example bevacizumab, radiation) can result in stroke

4.3 Supportive Care Guidelines

Appropriate supportive care during the duration of the study includes the following:

- Bevacizumab or steroid administration for neurologic symptoms arising from increased edema or intracranial pressure, which are presumed mechanisms of action for M032, will be allowed, if deemed appropriate and safe in the determination of the investigator. The increase in steroid dose will be kept to a minimum as patient neurologic condition permits. In general, UAB Neuro-oncology protocol is that Avastin is given every two weeks at a dose of 10/kg mg IV. Dosage adjustments or cessation of drug

may be made should adverse events (Uncontrolled hypertension, proteinuria, bleeding, thrombosis, etc.) occur and are made on a case-by-case basis by the prescribing neuro-oncologist.

- Proton pump inhibitors or H2 antagonists for control of steroid-induced gastric irritation
- Anti-epileptic medicines for control of partial or generalized seizures
- Post-operative neurological intensive care that is routine for the neurosurgical interventions involved in the administration of M032
- Other than a restriction on medications with anti-HSV activity (to be given only for the management of an adverse event), there are not any limitations on concomitant medications that patients may receive for other co-morbidities

Management of adverse events is discussed in **Section 5**.

4.4 Duration of Therapy/Study

The therapeutic intervention in this trial involves the administration of a single infusion of M032. For this reason it is more appropriate to define the duration of the study for each patient rather than the duration of therapy. All subjects participating in the study will be considered intent to treat and will be followed through all scheduled visits without concern for the total amount of study treatment received.

In regard to the evaluations of treatment efficacy or the acceptability of other treatments for the malignant glioma, the study will continue as scheduled until one of the following criteria applies:

- Disease progression (as defined in **Section 9**)
- Patient withdrawal from the study

Scheduled post-therapy safety evaluations as indicated in the study schedule will continue for every patient regardless of the response to M032. These evaluations will stop only if one of the following criteria applies:

- Disease progression (as defined in **Section 9**) has rendered the patient not evaluable
- Patient withdrawal from the study

4.5 Halting Rules for Study

Should 2 or more Grade 3 or Grade 4 toxicities not thought to be related to tumor, prior therapy or expected to be related to HSV occur in the same dose level, enrollment will be suspended until an evaluation of these toxicities has been conducted by the trials Data Safety and Monitoring Board (DSMB). The DSMB will be the arbiter as to whether these toxicities can be attributed to M032 and if so, invoke a stopping rule, halting enrollment. If the DSMB should feel that these toxicities are not related to M032 administration, enrollment will be reinstated as per its instructions. Should a particular DLT be evaluated by the DSMB and felt to be 1) consistent with M032 activity and 2) of acceptable duration and severity, the DSMB may decide to waive the DLT and/or enroll additional patients at this dose level due to the life-threatening nature of the underlying disease under study.

- The DSMB may interrupt study enrollment and entry at any time if medically indicated.
- If one (1) subject dies due to an event related to (caused by) the study intervention, study enrollment will be halted and enrollment may only begin after the DSMB reviews the data and the DSMB determines it is safe to continue.
- If two (2) subjects experience a Grade 4 toxicity using the NCTAE Toxicity Table, study enrollment will be halted and enrollment may only begin after the DSMB determines it is safe to continue.
- If two (2) instances of cytokine storms result in two instances of Grade 4 toxicity and/or uncontrolled corticoid steroids and acyclovir therapy are required, within the same cohort, study enrollment will be halted and enrollment may only begin after the DSMB reviews the data and the DSMB determines it is safe to continue.

- If two (2) or more grade 3 toxicities not thought to be related to tumor, prior therapy or expected to be related to HSV occurring in the same dose cohort, enrollment will be suspended until an evaluation of these toxicities has been conducted by the trial's DSMB. Enrollment may only begin after the DSMB reviews the data and the DSMB determines it is safe to continue.
- If two (2) or more Grade 4 neurologic toxicities not thought to be related to tumor, prior therapy or other treatment associated modalities occur in the same dose cohort, enrollment will be suspended until an evaluation of these toxicities has been conducted by the trial's DSMB. Enrollment may only begin after the DSMB reviews the data and the DSMB determines it is safe to continue.

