Subject Population:	8 to 24 patients with recurrent/progressive glioblastoma multiforme , anaplastic astrocytoma or gliosarcoma depending on toxicities. (Numbers may vary slightly pending acceptance of previously treated patients to update the CRM)
Study Medication and Dosage:	Dose escalations of up to, but not exceeding the next highest dose level (1 log). Dose escalations from 1×10^5 to 1×10^9 plaque-forming units of M032, a genetically engineered herpes simplex virus type 1 expressing human IL-12 (NSC 733972).
Safety Evaluations:	Follow-up evaluations using routine laboratory analyses and clinical measurements of neurological function and evidence of M032-related toxicity. Studies to evaluate the possibility of M032 shedding will also be conducted. Patients will be observed closely during the planned post-treatment hospitalization period, followed by outpatient evaluations done at 10 days, then months 1, 2, 3, 4, 5, 6, 9 and 12, subject to disease progression.
Study Endpoints	Primary: CRM-estimated highest safe dose or maximal planned dose if no dose-limiting toxicity observed. Secondary: Time to progression, survival, biologic assessments.

TABLE OF CONTENTS

Section	Page Number
SYNOPSIS	3
1. OBJECTIVES	6
1.1 Lay Abstract	6
1.2 Primary Objective	6
1.3 Secondary Objectives	6
1.4 Tertiary Objectives	6
2. BACKGROUND	6
2.1 Safety and efficacy of non-virulent, oncolytic $\Delta\gamma$134.5 HSV	6
2.2 Malignant Glioma	10
2.3 Rationale	11
3. PATIENT SELECTION	11
3.1 Eligibility Criteria	11
3.2 Exclusion Criteria	12
3.2 Inclusion of Women and Minorities	13
4. TREATMENT PLAN	13
4.1 Study Summary	13
4.2 Definition of Dose-Limiting Toxicity	18
4.3 Supportive Care Guidelines	20
4.4 Duration of Therapy	20
4.5 Halting Rules for Study	20
5. EXPECTED ADVERSE EVENTS/DOSE MODIFICATIONS	21
5.1 Expected Adverse Events Associated with M032	21
5.2 Dosing Delays/Dose Modifications	23
5.3 Adverse Assessment and management Assessment by PI/Clinician	23
6. AGENT FORMULATION AND PROCUREMENT	23
6.1 M032 Formulation and Storage	23
6.2 Availability	23
6.3 Excipient for Dilution of M032	24
6.4 M032 Dose Preparation	24
6.5 Precautions in Handling M032	24
6.6 Precautions in Disposal of M032	24
7. CORRELATIVE/SPECIAL STUDIES	24
8. STUDY CALENDAR	26
8.1 Study Procedures	27
9. MEASUREMENT OF EFFECT	33

9.1	Definitions	33
9.2	Guidelines for Evaluation of Measurable Disease	33
9.3	Response Criteria	34
9.4	Confirmatory Measurement/Duration of Response	35

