Three values for d_{90} will be chosen in this protocol with weights of one tenth that of real subject data. This allows flexibility in the upper end of the dose toxicity curve. This adaptation to the CRM came about after subject data demonstrated that d_{90} was incorrect in previous studies, because doses approaching d_{90} were tried with no toxicities observed. This situation required that d_{90} be moved to a higher dose or the fitted dose toxicity curve became too steep and no dose escalations resulted.

We assume the dose for $d_{10} = 1 \times 10^4$ pfu for M032 (**Table 1**). A set of three values will be chosen for $d_{90} = 1 \times 10^{15}$ pfu. These values for d_{90} spread probability mass over a wider range and may eliminate the need to increase d_{90} if the data are inconsistent with a single value. Based on these starting points, our desire is to employ a dose of virus to yield no more than 33% chance of clinical toxicity. The initial starting dose will be assumed to be 1×10^5 PFU and the maximum dose to be tested would be 1×10^9 PFU. Further assumptions would be that the maximum number of subjects would be 204 and that the dose cohort size would be 1. Further, the next CRM recommended log dose would be rounded to the nearest 0.5 or full dose. Moreover, the number of consecutive subjects at the maximum tolerated dose would be 10 or a number until 20 subjects are treated, whichever comes first. This will allow us to collect more information of the safety of the MTD. If a second toxicity is observed for patients on the highest dose, then the next lower dose is used and declared MTD if 10 consecutive subjects on the same dose are toxicity free or if n=20 is reached. If more toxicities are found, CRM will be used in the de-escalation of the dose.

The outcome space for the first CRM iterations would look like the values shown as six sample scenarios in **Table 2** using a starting dose 1×10^5 pfu. We will not allow dose escalations to exceed 10 times the maximum dose already administered. In this way, we prevent a too rapid dose escalation or testing high doses without a reasonable degree of certainty concerning their safety. Although the values in **Table 2** appear reasonable to us currently, we emphasize that they should not be taken literally. Indeed, if we receive approvals (DSMB, IRB, FDA), we will update the CRM model using the four patients previously enrolled and treated. Some of the data

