5. EXPECTED ADVERSE EVENTS/DOSE MODIFICATIONS

5.1 Expected Adverse Events Associated with M032

Although M032 has not yet been used in humans, the adverse events it might produce are expected to be similar to the adverse events observed in the Phase I trials of a similar genetically-engineered herpes simplex virus, G207. G207 caused no DLT and the adverse events that were observed following treatment were not thought to be attributable to the study drug.

Adverse events occurring after the administration of G207 included the following, which are therefore expected to possibly occur following M032:

- | | | |
|--------------------|------------------------------|---------------------------------|
| • asthenia | • hemiplegia | • dysphasia |
| • amnesia | • confusion | • depression |
| • nausea | • headache | • deep vein thrombosis |
| • somnolence | • decreased consciousness | • seizure |
| • leukopenia | • anemia | • abnormal erythrocytes |
| • peripheral edema | • cachexia | • urinary tract infection |
| • fever | • varicella zoster infection | • tumor progression |
| • pneumonia | • abnormal mentation | • increased liver transaminases |
| • death | • stroke | • pseudoprogression |

Other adverse events that might be expected based on the origin of M032 and on the patients' disease include the following:

- hematoma
- encephalitis
- hepatitis
- disseminated HSV infection
- allergic response to M032
- nuchal rigidity
- photophobia
- autoimmune response to CNS tissues

Any of the above adverse events will be considered a DLT, if possibly, probably or definitely attributable to M032 and if the severity of the adverse event is Grade 3 (in some situations) or Grade 4, as defined in **Section 4.2**.

Subjects will be observed closely for evidence of any adverse events. After the delivery of M032, subjects will be observed in a Clinical Research Unit bed, a step down unit or the Neurosurgical ICU per the discretion of the surgeon. The subjects' vital signs (temperature, blood pressure, pulse, respiratory rate) and neurologic function and limited neurological exam will be monitored every hour for the first twelve hours, then every two hours for the next 12 hours, then every 4 hours for the next 24 hours. Thereafter, the frequency of monitoring will be determined by the attending physician(s) based on the medical condition of the patient.

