- Disseminated HSV Infection: Disseminated multi-organ disease attributed to HSV is exceedingly uncommon, even in the immunocompromised host. Such disease has been encountered in the newborn with disease identified as 'disseminated multiorgan involvement' and occurs in about 25% of newborns with this disease (incidence 1:10,000 deliveries).[38] In adults, disseminated disease has been encountered in stem cell transplant recipients and, very rarely, pregnant women.[39] In all circumstances, disseminated disease is associated with a systemic host response of fever, and findings compatible with sepsis, including hepatic dysfunction. To monitor for these rare events, most importantly, serial physical examinations will be performed to assess for fever and symptoms of sepsis or hepatic dysfunction. In addition, serial blood specimens will be obtained at Days 2, 10, 28 and monthly thereafter and cultured for infectious HSV. Any positive cultures will be analyzed by PCR to discriminate between wild type HSV-1 and mutant M032 HSV. Should a patient develop fever, rash, or unexplained elevations in liver function tests in conjunction with a concomitant increase of infectious HSV by plaque assay in blood specimens (exceeding prior values by 2 logs), patients will undergo a 21 day course of treatment with acyclovir for presumed disseminated HSV infection. Parenthetically, it should be noted that oncolytic HSV therapy for metastatic colon carcinoma involving the liver led to detectable HSV DNA in the blood but in the ABSENCE of clinical symptomatology[40]; thus, increasing levels as well as fever will both be required to therapeutically intervene. Should 2 Grade 3 or 4 toxicities attributable to disseminated HSV infection occur in the same dose level, the prior dose level shall be declared the MTD and enrollment will be halted.

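### The Grade 3 suspension trigger in Section 4.5 can be read to leave out HSV-type toxicity of an HSV study drug, and its counting unit is not fixed

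*Combined protocol and SAP*

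**What the plan says.** All references are to the combined protocol and SAP.

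- **Trigger, Section 4.5.** The opening sentence suspends enrollment for two or more Grade 3 or 4 events, limited to "toxicities not thought to be related to tumor, prior therapy or expected to be related to HSV". A later bullet repeats the limit for Grade 3 events alone. The opening sentence counts events as "prior therapy or expected to be related to HSV occur in the same dose level"; the bullet counts them as "expected to be related to HSV occurring in the same dose cohort". The DSMB then decides whether the counted events are attributable to M032. It may also waive a DLT that it finds consistent with M032 activity and acceptable in duration and severity.
- **Study drug, synopsis.** M032 is "a genetically engineered herpes simplex virus type 1 expressing human IL-12".
- **Expected events, Section 5.1.** Under "Other adverse events that might be expected based on the origin of M032" and on the patients' disease, the list includes encephalitis, hepatitis and disseminated HSV infection. The section makes listed events DLTs when attributable to M032 and severe enough under Section 4.2. Neither section has an HSV exception.
- **Disseminated HSV, Section 5.1.** This section has its own rule, which begins "Should 2 Grade 3 or 4 toxicities attributable to disseminated HSV infection occur in the same dose level, the prior dose level shall be declared". Under it, that earlier level becomes the MTD and accrual stops. No DSMB step is mentioned.
- **Cohort size.** Section 4.1.1 assumes "the dose cohort size would be 1", and also up to 10 subjects at the putative MTD. The synopsis allows up to 3 per level, Section 4.2 speaks of a second and third patient at a level, and Section 11 uses a three-at-one design until the first DLT.

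**The concern.** A suspension rule for an oncolytic HSV should at least count the toxicities that the agent is most likely to cause. If the HSV phrase is a third exclusion beside tumor and prior therapy, the events most specific to M032 drop out of the count before the DSMB is asked whether M032 caused them. If the phrase adds HSV events, the rule means the reverse. Staff who must decide whether to suspend enrollment cannot tell which from the text.

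The count also depends on how many subjects share a level or cohort, and the plan gives several answers. With one subject per level, two different subjects can never meet the rule. What is at stake is whether drug-related Grade 3 events during dose escalation lead to a mandatory pause or only to discretionary review.

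**Working it through.** The plan states no operating characteristic for the halting rules, so there is no figure to reproduce. The check sets the sections side by side and then works out what the counting unit does.

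**1. Two readings of the HSV phrase.**
- *Exclusion.* HSV is the third item after tumor and prior therapy. The Grade 4 neurologic bullet in 4.5 and the neurologic rule in 5.3 have the same three-part form, and their third item (other treatment-related modalities) is plainly an exclusion. This is the natural reading.
- *Inclusion.* Events expected from HSV are added to the count. This fits better with the DSMB's next task of judging attribution to M032, and with its power to waive events consistent with M032 activity.

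The text does not settle it.

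**2. What a mandatory trigger catches on the exclusion reading.**

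| M032-related events | 4.5 Grade 3 trigger | Other mandatory trigger |
|---|---|---|
| Two Grade 3 hepatitis events, one level | not counted | none found |
| Two Grade 3 encephalitis events, one level | not counted | 5.3, if classed as neurologic DLTs |
| Two Grade 3 disseminated-HSV events, one level | not counted | 5.1 |
| Grade 4 events in two subjects, any levels | not needed | 4.5 Grade 4 bullet |
| One related death | not needed | 4.5 death bullet |
| One Grade 3 event at each of two levels | not counted | none found |

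The last row holds on either reading. The disseminated-HSV, neurologic and cytokine-storm rules are likewise tied to one level or cohort.

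**3. Effect of the number of subjects at a level.** For n independent subjects, each with probability p of a counted event, the chance that at least two are affected is 1 − (1−p)^n − np(1−p)^(n−1).

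Inputs: p = 1/3, the target toxicity probability in 4.1.1, used only as an illustration, with an assumed range of 0.10 to 0.50. The values n = 1, 3 and 10 come from the stated cohort sizes; n = 2 is an intermediate case.

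| p | n=1 | n=2 | n=3 | n=10 |
|---|---|---|---|---|
| 0.10 | 0 | 0.010 | 0.028 | 0.264 |
| 1/3 | 0 | 0.111 | 0.259 | 0.896 |
| 0.50 | 0 | 0.250 | 0.500 | 0.989 |

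For example, with n = 3 and p = 1/3: 1 − 0.2963 − 0.4444 = 0.259.

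The share of events that would be excluded as HSV-expected is not given. If it were half, p falls from 1/3 to 1/6. At n = 3 the result is 1 − 0.5787 − 0.3472 = 0.074, and at n = 10 it is 0.515. If all were excluded, both are 0. The n = 10 column assumes all ten subjects are treated at that level, which the CRM would not allow after enough toxicity.

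**4. Subjects per level in Table 2.** In the rows printed, log doses 5, 6 and 7 have one subject in all six scenarios, and 7.5 has one in five of six. Log dose 8 has 2 to 5 subjects, and the level declared MTD has 5 to 11. Section 4.1.1 warns against taking these values literally.

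**5. How the CRM reacts to a DLT.** I refitted the logistic model to Table 1 (weighted binomial likelihood, pseudo-data at weight 0.5, real subjects at an assumed weight of 1, target 0.33 to 1/3).
- Initial recommendation: 6.69 to 6.71, against 6.7842 stated.
- With no DLTs: about 6.9, 7.2, 7.6 and 8.0 after subjects 1 to 4. With the one-log cap and half-log rounding this gives 5, 6, 7, 7.5, 8, as in Table 2.
- With a first DLT in subject 1, 2, 3 or 4: about 3.9, 5.6, 6.4 or 7.0.

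The refit is approximate. After five clear subjects it gives about 8.3, which rounds to 8.5 where Table 2 has 8.

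**6. Two disseminated-HSV events at one level.** Section 5.1 halts enrollment and fixes the prior level as the MTD. On the exclusion reading, 4.5 ignores Grade 3 cases, so only 5.1 applies to them; Grade 4 cases in two subjects still go to the DSMB under the separate bullet. On the inclusion reading, 4.5 suspends at both grades pending the DSMB, which may reinstate enrollment or waive the DLT. Rewording 4.5 to count these events therefore makes the conflict with 5.1 live at Grade 3 as well.

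**The case against.** The strongest reply is that 4.5 is not the main brake. Under 4.2 the Medical Monitor and DSMB review the safety of each dose, after at least 24 days, before the next level opens. Section 10.2 adds quarterly and real-time review, and 4.5 lets the DSMB interrupt at any time. DLTs carry no HSV exception and lower the CRM recommendation. All of this stands, and it narrows the gap. It does not replace a stated mandatory trigger, and it does not tell staff which reading of the phrase to apply.

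The reply can add that the rule counts toxicities rather than subjects, so two events in one subject could meet it even with one subject per level. Literally that is so, which is one more reason to name the unit.

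Three stronger readings are tempting and are not supported:
- A reader might put a 33% risk on each of the first five subjects in Table 2, who sit on five levels, and conclude that two or more would have a DLT without meeting the count with probability 1 − 0.67^5 − 5(0.33)(0.67^4) = 0.53. That path requires subjects 1 to 4 to be DLT-free if the CRM is followed (step 5), so two DLTs cannot occur on it. Section 11 also adds a patient at the same dose after the first DLT.
- A reader might infer that no Grade 3 toxicity of M032 is counted, or that the trial has no brake during escalation. Only HSV-expected events are in question, 5.1 catches disseminated HSV at one level, and DSMB review precedes each step up.
- A reader might take one subject per cohort as settled, or 4.2 as a third conflicting action. Cohort size is stated in several ways, and the DLT definition in 4.2 prescribes no halting action for these events.

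**Conclusion.** The point holds in limited form. The Grade 3 trigger in 4.5 either omits HSV-type toxicity of an HSV agent, contrary to the DLT definitions in 4.2 and 5.1, or has two opposite meanings. Either way a safety rule cannot stand as written.

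On the exclusion reading, the gap in mandatory suspension is mainly Grade 3 HSV-type events outside disseminated infection and neurologic DLTs, with hepatitis the clearest case. On any reading, it also includes Grade 3 events spread over successive levels. Separately, the counting unit is undefined: the chance that two subjects at one level are affected runs from 0 to 0.90 across the stated sizes at p = 1/3. Those values assume independent subjects and a common risk, and they show sensitivity only. The plan gives no basis for an overall probability that the rule misses harm, and none is claimed. The actions for disseminated HSV in 4.5 and 5.1 conflict at Grade 4 on either reading, and at Grade 3 on the inclusion reading.

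**What to change.** 1. In both places in 4.5, reword the HSV phrase so that it does not exclude the M032-related events that 4.2 and 5.1 count as DLTs.
2. Reconcile 4.5, 5.1 and 5.3 so that one action is stated for disseminated HSV infection, including whether the DSMB decides. Do this together with item 1, because the rewording brings the two rules into direct conflict at Grade 3.
3. State one counting unit: toxicities or subjects, dose level or dose cohort. Make it consistent with a single cohort size across the synopsis and Sections 4.1.1, 4.2 and 11, and say how events on different levels are treated.

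No threshold or clinical action is proposed here; those are for the sponsor and the DSMB. The cost is wording in an amendment, and possibly one or two more DSMB reviews.
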